## 11.3. Clinical Laboratory Data

The hematology, clinical chemistry, coagulation, PRA, TSH, and free T4 data will be summarized with descriptive statistics by treatment group and visit. Both observed values and changes from baseline will be summarized for the DB period and OL period separately.

Shift tables will be presented for selected clinical laboratory variables based on the reference range-based categories of "Low," "Normal," or "High." A clinical laboratory variable value will be assigned to one of these three categories according to the reference ranges provided by the central clinical laboratory.

A table of shifts from baseline to Week 28 will be presented within the double-blind treatment period. Each shift table will have four rows and four columns, with rows reflecting the reference range category at baseline (or missing if applicable), and columns reflecting the reference range category at the specified postbaseline visit (or missing if applicable). A "Total" row and "Total" column will also be included. The number and percentage of subjects in each shift category will be displayed in the table; percentages will be based on the number of subjects included in the table. Two additional shift tables will be presented within the OL period: shifts from baseline to Week 52 and shifts from OL baseline to Week 52.

Shift tables will be presented for the following clinical laboratory variables:

- aspartate aminotransferase (AST),
- alanine aminotransferase (ALT),
- alkaline phosphatase (ALP),
- total bilirubin,
- creatine kinase,
- creatinine,
- white blood cell count,
- absolute neutrophil count,
- hemoglobin,
- platelet count,
- TSH,

- Free T4, and
- PRA.

## 11.4. Vital Signs

The vital signs data (blood pressure [BP], pulse rate, respiratory rate, and body temperature) will be summarized with descriptive statistics by treatment group and visit. Sitting blood pressure and heart rate measurements were collected in triplicate at each visit throughout the study and the average of the triplicate values will be used for the purpose of summarization. Observed and change from baseline values for pulse rate, respiratory rate, and body temperature will be summarized for the DB period and OL period separately.

Blood pressure data will be summarized categorically based on the guidance published by Flynn et al (Flynn 2017) for subjects with normal blood pressure, elevated blood pressure, stage 1 HTN (hypertension), and stage 2 HTN (as defined in Table 8 below). Percentiles for systolic blood pressure and diastolic blood pressure will be calculated based on the boys and girls tables (by age and height percentile) as published by Flynn et al (Flynn 2017). The number and percentage of subjects in each of the following blood pressure categories will be presented by treatment group and visit by age category as well as all ages combined:

	Ages 2 - < 13 years old	Subjects ≥ 13 years old	
Normal BP	< 90 th percentile	<120/<80 mm Hg	
Elevated BP	$\geq$ 90 th percentile to < 95 th percentile or 120/80 mm Hg to < 95 th percentile (whichever is lower)	120/<80 to 129/<80 mm Hg	
Stage 1 HTN	$\geq$ 95 th percentile to < 95 th + 12 mm Hg or 130/80 mm Hg to 139/89 mm Hg (whichever is lower)	130/80 to 139/89 mm Hg	
Stage 2 HTN	$\geq$ 95 th percentile + 12 mm Hg or 140/90 mm Hg (whichever is lower)	$\geq$ 140/90 mm Hg	

Table 8	: Blood	Pressure	Categories	by	Age	Group
				•		1

Flynn et al., 2017.

The same categorical summaries will be presented in frequency tables for the maximum value at any postbaseline visit within the treatment period (including unscheduled and early termination visits). Each subject will be counted once by their maximum postbaseline blood pressure category. The above categories will be summarized for both the DB and OL periods.

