## 9.7.3. Vital Sign Measurements

Vital sign measurements, including systolic and diastolic blood pressure, pulse rate, respiratory rate, and body temperature (oral, rectal, ear, or forehead), as well as body weight will be measured. Blood pressure and pulse rate will be measured 3 times, in up to 1-minute intervals,

using a Sponsor-provided, age-appropriate, calibrated automatic blood pressure cuff (with the exception of at-home visits) after the subject has been sitting quietly for at least 5 minutes.

Vital sign measurements will be obtained as specified in Table 7 and Table 8.

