## APPENDIX A. GLUCOCORTICOID STRESS DOSING GUIDANCE

Extra glucocorticoid (eg, hydrocortisone) must be given during times of **extreme physical stress** such as fever, vomiting and diarrhea, surgery, and significant trauma (eg, broken bones and concussions) (CARES Foundation, 2014; Miller et al., 2020; National Institutes of Health). The fludrocortisone dose does not need to be changed.

Type of Illness	Instruction		
Minor illness or low-grade fever >100.5°F (38°C):	Double the hydrocortisone dose for the entire day, until fever or symptoms subside. Drink extra fluids (sugar- and salt-containing).		
Moderate illness or fever ≥102°F (39°C)	Triple the hydrocortisone dose for the entire day (administered in 3 to 4 divided doses over the day) until fever or symptoms subside.  Drink extra fluids (sugar- and salt-containing).		
Vomiting	Triple the hydrocortisone dose.  If vomiting occurs <30 minutes after taking the dose, wait 15 to 30 minutes and repeat the dose since it was likely not absorbed.  If vomit again, administer injectable hydrocortisone (Solu-Cortef) (see below) and contact treating physician. Do not delay in giving injectable hydrocortisone.		
Diarrhea	If no fever and feeling well, no need for stress dosing.  If not feeling well, double the hydrocortisone dose.  Drink extra fluids (sugar- and salt-containing).		
All illnesses	To prevent dehydration, drink extra sugar and salt-containing fluids (eg, nondiet soda, Gatorade, popsicles, soup).		
For minor surgical procedures not requiring general anesthesia	Triple the morning glucocorticoid dose.		
Not tolerating oral medications or unconscious	Administer injectable (eg, intramuscular) hydrocortisone (Solu-Cortef) at 50 to 100 mg/m² or doses below and contact the treating physician.  <3 years: 25 mg 3-12 years: 50 mg  >12 years: 100 mg  If unable to tolerate fluids or unconscious, contact emergency services for evaluation following injectable hydrocortisone treatment.		

- 1. Signs of acute cortisol deficiency (adrenal crisis) include, but are not limited to: headache, nausea, vomiting, abdominal pain, dehydration, confusion, weakness, lethargy, pallor, fatigue, dizziness, hypotension, hypoglycemia.
- Prevention of adrenal crisis: The injectable form of hydrocortisone (Solu-Cortef) must be kept at home and at school for emergencies. It may be kept in a medication cabinet for several years in the unmixed form. Check the expiration date and get a prescription refill when needed.

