### 4.6. Safety

Safety endpoints in the DB and OL periods include:

- Occurrence of treatment-emergent adverse events (TEAEs), exposure-adjusted subject incidence rate, serious adverse events (SAEs), severe TEAEs, adrenal insufficiency TEAEs, TEAEs leading to glucocorticoid stress dosing, and TEAEs leading to discontinuation from study drug
- Observed and changes from baseline in clinical laboratory test values (including hematology, clinical chemistry, thyroid stimulating hormone [TSH], free T4, plasma renin activity [PRA], and coagulation)
- Observed and changes from baseline in vital sign values
- Observed and changes from baseline in 6- or 12-lead electrocardiogram (ECG) intervals
- Observed and changes from baseline in total scores from the Brief Psychiatric Rating Scale for Children (BPRS-c)
- "Yes" responses to suicidal behavior or ideation at postbaseline assessments from the Columbia-Suicide Severity Rating Scale (C-SSRS; only for subjects ≥6 years of age)

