# 6. GENERAL CONSIDERATIONS FOR DATA ANALYSES AND HANDLING

### 6.1. General Statistical Procedures

All analyses described in this plan are considered a priori analyses in that they have been defined prior to locking the study database for the Week 28 analysis. Analyses defined subsequent to locking the database will be considered post hoc analyses and will be applied as exploratory methodology. Any post hoc analyses will be statistically justified and described as appropriate in the CSR. Statistical analysis will be conducted, and all tables, figures, and listings generated using SAS® software (version 9.4 or later), unless stated otherwise.

Unless otherwise noted, data from the double-blind, placebo-controlled period (Day 1 to Week 28; "DB period") will be summarized by randomized treatment group, defined as crinecerfont or placebo (DB treatment group). Data from the open-label period (Week 28 to Week 52; "OL period") will be summarized by OL treatment group, defined as placebo/crinecerfont or crinecerfont/crinecerfont to describe the subject's randomized treatment assignment and their OL treatment, as well as all subjects combined. Note that while crinecerfont (and matching placebo) dose levels (25 mg bid via oral solution for subjects 10 to <20 kg, 50 mg bid via oral solution for subjects 20 to <55 kg, or 100 mg bid via oral capsules for subjects  $\geq$ 55 kg) are assigned based on weight at Day 1 and again at Week 28, summaries of the DB and OL period data will not be broken out by dose level unless otherwise specified.

Descriptive and inferential statistical methods will be used to evaluate and summarize the data from this study. The term "descriptive statistics" refers to the number of subjects (n), mean, median, standard deviation (SD) or standard error (SE), minimum, and maximum for continuous variables. Ordinal categorical data will be summarized using median, minimum and maximum values. Number and percentage of subjects will be summarized for categorical variables. The term "inferential statistics" refers to hypothesis tests that will be performed to assess differences between the treatment group and the control group. All hypothesis tests will be tests of the null hypothesis of no difference between the groups being compared versus the two-sided alternative hypothesis that there is a difference. The level of significance (type I error) for declaring statistical significance will be 0.05.

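### SAP 11.4 does not carry out change from baseline for blood pressure although SAP 4.6 lists it, and its category tables count a low reading as Normal BP

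*SAP*

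**What the plan says.** SAP 4.6 lists among the safety endpoints for both the double-blind (DB) and open-label (OL) periods: "Observed and changes from baseline in vital sign values". It makes no exception for BP. Protocol 9.7.3 defines the term: "Vital sign measurements, including systolic and diastolic blood pressure, pulse rate, respiratory rate, and body temperature".

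SAP 11.4 then plans four summaries:

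- By-visit descriptive statistics, with BP included: "The vital signs data (blood pressure [BP], pulse rate, respiratory rate, and body temperature) will be summarized with descriptive statistics by treatment group and visit". SAP 6.1 defines descriptive statistics to include "minimum, and maximum for continuous variables".
- Change from baseline, with BP absent: "Observed and change from baseline values for pulse rate, respiratory rate, and body temperature will be summarized for the DB period and OL period separately".
- BP categories by arm, visit and age group, from SAP Table 8: Normal, Elevated, Stage 1 and Stage 2 hypertension. Normal is anything under the 90th percentile for ages 2 to under 13, and anything under 120/80 mm Hg from age 13. Neither cell has a lower bound.
- The same categories over all postbaseline visits, unscheduled and early termination visits included: "Each subject will be counted once by their maximum postbaseline blood pressure category".

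Protocol Appendix A includes among the signs of acute cortisol deficiency "dehydration, confusion, weakness, lethargy, pallor, fatigue, dizziness, hypotension, hypoglycemia".

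**The concern.** The trial lowers glucocorticoid by design after Week 4, and its own appendix treats low BP as a sign of too little glucocorticoid. The category tables that SAP 11.4 builds for BP look in the other direction. If the section is programmed as written, the DB and OL safety outputs will count children with high BP by arm but will not count children with low BP, and one listed safety endpoint will not be produced for BP. A reader of the study report could then take a high proportion in Normal BP as reassurance about hypotension, which that category cannot give.

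**Working it through.** The plan states no figure on this point that could be reproduced. The check sets the sections side by side and applies the Table 8 rule.

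**1. Change from baseline.**

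| Source | BP included? |
|---|---|
| SAP 4.6, change from baseline in vital signs | Yes, by the general term |
| Protocol 9.7.3, definition of vital signs | Yes, systolic and diastolic |
| SAP 11.4, by-visit descriptive statistics | Yes |
| SAP 11.4, change-from-baseline sentence | No |
| SAP 14, assessments not to be summarized | BP not listed |

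The endpoint is listed in 4.6 and not carried out in 11.4. SAP 14 gives no sign that this was deliberate.

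**2. Category rule.** For subjects aged 13 or over, the rule is Normal if systolic <120 and diastolic <80. The values below are assumed, to exercise the rule; they are not trial data.

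- 110/70, 90/55, 80/45, 70/40 and 60/30 all classify as Normal.
- Child A has baseline 112/70, then 78/42 and 110/68. Each visit is Normal and the maximum category is Normal.
- Child B has baseline 112/70, then 78/42 and 124/76. The maximum category is Elevated.

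In both children systolic pressure falls by 112 − 78 = 34 mm Hg. Child A is tabulated as Normal throughout, and in the any-visit table Child B appears only as a raised value. For ages 2 to under 13 the result is the same in kind, because a cell defined as below the 90th percentile has no floor.

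**3. What the other outputs recover.**

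- *By-visit minimum.* The value 78 enters the descriptive statistics and appears as the minimum if it is the lowest in that arm and visit. That is one raw mm Hg value pooled over ages 2 to 17. SAP 11.4 itself grades children under 13 by percentiles that depend on sex, age and height, so the pooled minimum may simply be a small child's ordinary reading. It is not a count of children.
- *Unscheduled readings.* Where one observation per visit is needed, SAP 6.7 keeps the one nearest the target day. An unscheduled low reading can drop out of the by-visit tables. The maximum table takes in unscheduled visits explicitly; nothing does so for low values.
- *Adverse events.* SAP 11.2, 11.2.3 and 11.2.4 tabulate treatment-emergent events, acute adrenal insufficiency and stress dosing. They depend on an event being reported. Protocol 11.1 asks for the diagnosis and not its separate signs, so hypotension within another diagnosis may not be coded. The adrenal table searches one preferred term.

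**4. Comparison within the SAP.** The laboratory shift tables in SAP 11.3 use low, normal and high categories. The BP tables have no low category.

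**The case against.** The strongest reply is that low BP is covered elsewhere and better. BP is named first in the by-visit statistics, and these show the minimum. A clinically significant fall is an adverse event, with separate tables for adrenal insufficiency and for stress dosing by severity. A checklist for insufficiency precedes dose reductions in the placebo-controlled period, and the data monitoring committee reviews stress-dosing events. After glucocorticoid reduction starts at about Week 6, scheduled DB vital signs fall only at Weeks 16 and 28, so clinic BP would often miss an acute crisis. Upward categories also have a reason: Protocol 5.1 names hypertension as a harm of supraphysiologic glucocorticoid, and every child enters on more than 12 mg/m²/day.

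Much of this stands, and it rules out several stronger readings that a reader might infer:

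- *That change from baseline in BP was never planned.* SAP 4.6 lists it; the fault is a conflict with 11.4.
- *That the BP outputs can show only high values, or that a hypotensive child is reported solely as normal.* The by-visit statistics and the adverse-event tables say otherwise. The statement is true of the category tables only.
- *That low BP is the trial's main known risk.* Protocol 9.7.2 considers glucocorticoid insufficiency unlikely at the target doses.
- *That the postural dizziness listed in Protocol 5.2 supports the point.* BP is measured sitting, and the same section reports no safety concern for vital signs.

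The reply does not supply the two missing outputs: change from baseline in BP, and a count by arm of children with low measured BP.

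**Conclusion.** The point holds in two parts. First, SAP 4.6 and 11.4 conflict, and as 11.4 is written the listed change-from-baseline endpoint is not produced for BP. This rests on the text alone. Second, in the category tables a low reading counts as Normal BP, and the only across-visit table uses the maximum. Other outputs cover this in part, but none counts children with low BP by arm.

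The size is modest. SAP 11 makes safety descriptive with no hypothesis testing, so no error rate, power or efficacy result changes. The documents give neither a BP standard deviation nor an expected frequency of low BP, so the number of children affected cannot be estimated. The second part assumes that a low-BP count is worth having in a trial that reduces glucocorticoid; Appendix A supports that by naming hypotension. The change should be made, but it is not critical to the trial's conclusions.

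**What to change.** In SAP 11.4:

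1. Add systolic and diastolic BP to the observed and change-from-baseline summary for the DB and OL periods, so that it agrees with SAP 4.6.
2. Split a Low BP category out of Normal in Table 8. The documents give no lower limit, so the sponsor must choose an age-appropriate one and prespecify it before unblinding.
3. Tabulate each subject's minimum postbaseline category beside the maximum, by arm and period, with unscheduled visits included as they already are for the maximum.

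Low BP here is a reporting category. It is not a clinical rule and implies nothing about dosing or management.

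The cost is a few extra descriptive tables and the work of choosing and justifying a limit. Protocol 9.7.3 already requires BP in triplicate, so no new data are needed.

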# 11.5. 6- or 12-lead Electrocardiogram

Descriptive statistics for the observed values and changes from baseline will be presented for each of the ECG parameters (heart rate, PR interval, QRS duration, QT interval, QTcF) by visit and treatment group.

Frequency tables (number and percentage of subjects) will be presented for the investigator overall categorical assessment (ie, Normal, Abnormal not Clinically Significant, or Abnormal Clinically Significant) by visit and treatment group.

Two additional categorical summaries (frequency tables displaying number and percentage of subjects) will be presented for the QTcF interval by treatment group. For the first summary, the observed QTcF values at each visit will be classified as follows:

- Greater than 450 msec
- Greater than 480 msec
- Greater than 500 msec

For the second categorical summary, the changes from baseline to each subsequent visit will be classified as follows:

- Increase greater than 30 msec
- Increase greater than 60 msec

The same categorical summaries will be presented in frequency tables for values at any postbaseline visit (including unscheduled and early termination visits) meeting the aforementioned criteria.

The above ECG summaries will be produced for the DB period and the OL period separately.

## 11.6. Columbia-Suicide Severity Rating Scale

The C-SSRS is a validated instrument to prospectively assess suicidal ideation and behavior and will be used only for subjects  $\geq 6$  years of age. The C-SSRS data will be presented in the following summaries:

- Screening/lifetime assessment
- Screening/past 6 months (suicidal ideation items); past 1 year (suicidal behavior items) assessment
- Baseline (Day 1) assessment
- Postbaseline assessments

Each summary will display the number and percentage of subjects who report "Yes" to specific C-SSRS items or categories of items (a category is assigned a "Yes" value if a "Yes" is reported for any item in the category). These C-SSRS items and categories are as follows:

- Suicidal Ideation Items
  - (1) Wish to be dead
  - (2) Non-specific active suicidal thoughts
  - (3) Active suicidal ideation with any methods (not plan) without intent to act
  - (4) Active suicidal ideation with some intent to act, without specific plan
  - (5) Active suicidal ideation with specific plan and intent
- Suicidal Ideation Category: Any of items (1) through (5)
- Suicidal Behavior Items
  - (6) Preparatory acts or behavior

- (7) Aborted attempt
- (8) Interrupted attempt
- (9) Non-fatal suicide attempt
- (10) Completed suicide ("Since Last Visit" assessments only)
- Suicidal Behavior Category: Any of items (6) through (10)
- Suicidal Ideation or Behavior Category: Any of items (1) through (10)

For the "all postbaseline assessments" summary, each subject's C-SSRS responses for all postbaseline assessments will be evaluated, and a "Yes" response for any assessment will be considered as a "Yes" for the subject.

In addition to the summaries described above, shift tables comparing postbaseline suicidal ideation scores to baseline scores will be presented. The shift table scores are defined as the following:

- 0 = No suicidal ideation
- 1 =Wish to be dead
- 2 = Non-specific active suicidal thoughts
- 3 = Active suicidal ideation with any methods (not plan) without intent to act
- 4 = Active suicidal ideation with some intent to act, without specific plan
- 5 = Active suicidal ideation with specific plan and intent

The shift tables will display the number and percentage of subjects within each cell of a  $6 \ge 6$  table for each treatment group, with the rows representing the baseline score and the columns representing the maximum score recorded across all postbaseline assessments (including both scheduled and unscheduled visits). Subjects missing either a baseline score or all postbaseline scores will not appear in the table.

The above C-SSRS summaries will be produced for the DB period and the OL period separately.

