- Day 1 and Weeks 4, 28, and 52/ET: at approximately 0600 hours, at approximately 0800 hours prior to dosing with morning GC and (after Day 1) study drug and at approximately 3 and 6 hours after dosing, and within 30 minutes prior to the evening dose of GC; if subject is not on an evening GC dose, then prior to bedtime. Any midday GC dose that the subject is receiving should be taken after the salivary sample collection 6 hours after dosing.
- Weeks 8, 12, 16, 20, 32, 36, 40, 44, and 56: prior to morning GC dose at approximately the same time as the blood sample. If a blood sample is not obtained at a visit (eg, because no GC dose adjustment was required), a salivary sample does not need to be obtained.
- m Subjects should take their GC dose the night before prior to 2100 hours and hold their morning dose of GC, fludrocortisone (if applicable), and study drug (except screening) until after predose blood sample collection. The blood sample collection will include 17-OHP and A4 at all visits, and will also include ACTH at Weeks 16, 28, 40, 52/ET, and 56. Morning dosing should occur between approximately 0800 and 0830 hours with breakfast. At Week 28 and Week 52/ET, another blood sample will be collected at 3 hours after dosing for subjects ≥6 years of age with body weight ≥20 kg.
- n Only in females with the most recent prior bone age <14 years and males with the most recent prior bone age <16 years. Bone age assessment is not required at the ET visit if the subject had a bone age assessment within 3 months prior.
- Only in male subjects. Week 28 and Week 52/ET ultrasound only if testicular adrenal rest tumor(s) demonstrated on Day 1. Testicular ultrasound is not required at the ET visit if the subject had a testicular ultrasound within 3 months prior.
- p EQ-5D-Y for age 8 to 15 years, EQ-5D-5L for age 16 years and older.
- q PedsOL Toddler Version for age 2 to 4 years, Young Child Version for age 5 to 7 years, Child Version for age 8 to 12 years, Adolescent Version for age 13 to 17 years.
- r Only for subjects ≥3 years of age.
- S Only for subjects >6 years of age. Baseline/Screening version used at screening, and Since Last Visit version at subsequent visits.
- t Hirsutism scale only for females.
- u Menstrual Cycle Ouestionnaire only for females who have undergone menarche and are not on hormonal or intrauterine device contraceptives.

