## 9.8. Specific Study Period Information

## 9.8.1. Screening Period (Week -4 to Day -1)

## 9.8.1.1. Screening Visit

All parents or legal guardians will provide informed consent with signed and witnessed pediatric assent for subjects determined by the investigator to be capable of providing assent according to national laws and regulations before the performance of any study-related procedures. Subjects will undergo screening for up to 4 weeks (Week -4 to Day -1) to determine eligibility. The screening period can be extended by up to 4 weeks after discussion with and approval of the Medical Monitor to allow for delayed screening laboratory results that are needed to determine eligibility or to accommodate other extenuating logistical issues, such as scheduling. After informed consent and assent have been obtained, subjects will be asked to take their evening glucocorticoid dose (the night before the visit) prior to 2100 hours and hold their morning dose of glucocorticoid and fludrocortisone (if applicable) until after blood sample collection, with dosing to occur between approximately 0800 and 0830 hours. During the screening period, blood sample collection may be performed at home.

- Obtain informed consent/pediatric assent.
- Assess inclusion/exclusion criteria.
- Review and record medical history.
- Perform a physical examination, including Tanner stage. Historical assessment of Tanner staging is acceptable if Tanner stage 5 has been previously documented.
- Perform vital signs, including height and weight.
- Collect blood samples for TSH; serum pregnancy test only for subjects of childbearing potential; chemistry, hematology, and coagulation labs; 17-OHP, A4,

<sup>a Values in parentheses refer to subjects whose evening crinecerfont dose is doubled in the setting of inadequate efficacy, because they will have blood tests approximately 1 month later.

cortisol, LH, FSH, testosterone, and PRA (prior to morning glucocorticoid and [if applicable] fludrocortisone dose).

- Collect urine for urine drug screen (only for subjects ≥12 years of age) and urinalysis.
- Administer the BPRS-c (only for subjects ≥3 years of age) and C-SSRS (Screening/baseline version; only for subjects ≥6 years of age).
- Perform 6- or 12-lead ECG.
- Provide eDiary to record daily glucocorticoid doses.

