- Collect salivary samples for hormone assessment at approximately 0600 hours, at approximately 0800 hours prior to morning glucocorticoid dosing and 3 and 6 hours after dosing, and within 30 minutes prior to the evening dose of glucocorticoid; if subject is not on an evening glucocorticoid dose, then prior to bedtime.
- Perform x-ray to assess bone age (only in females with the most recent bone age <14 years and in males with the most recent bone age <16 years; see Section 9.3.4).
- Perform testicular ultrasound (males only).
- Administer the EQ-5D (EQ-5D-Y for age 8 to 15 years, EQ-5D-5L for age 16 to 17 years); the PedsQL (PedsQL Toddler Version for age 2 to 4 years, Young Child Version for age 5 to 7 years, Child Version for age 8 to 12 years, Adolescent Version for age 13 to 17 years); and the PedsQL Family Impact.
- Administer the BPRS-c (only for subjects ≥3 years); and the C-SSRS (Since Last Visit version; only for subjects ≥6 years).
- Administer the Hirsutism (female subjects only) and Acne Scales.
- Review the Menstrual Cycle Questionnaire (only females who have undergone menarche and are not on hormonal or intrauterine device contraceptives).
- Perform 6- or 12-lead ECG.
- Dispense study drug: first dose to be taken at home with the subject's evening meal; thereafter, study drug will be administered bid with the subject's breakfast and evening meal (each dose separated by approximately 12 hours).
- Record concomitant medications.
- AE monitoring.

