#### 6.3.1. Baseline Definition for Analyses of DB Period Data

Other than the definitions described in Sections 6.3.3 through 6.3.5, the assessments collected on Day 1 prior to the first dose of study drug in the DB period will serve as the baseline value for all assessments through Week 28 of the study. If a Day 1 baseline value is not available, then the last measurement collected prior to study drug will serve as baseline. Bone age and testicular ultrasound assessments obtained within 1 month of Day 1 may serve as the baseline value if needed, as these parameters are not expected to change to a degree that could be clinically

detected over this time frame. This is considered the study baseline and will be referred to as "baseline" throughout this document.

Note that for serum hormone parameters that are collected both pre- and post-glucocorticoid (GC) dose, two baselines will be derived for all postbaseline pre-GC dose and visit average values where a change from baseline calculation is necessary, unless otherwise specified. Baseline pre-GC dose will be defined as the average of the pre-GC dose values (when collected more than once) or the single pre-GC dose value collected prior to study drug dosing. Baseline average will be defined as the average of serial sampling values collected prior to study drug dosing. If the Day 1 values are missing, the last measurement collected prior to study drug dosing will only be used as baseline average only.

For salivary hormone parameters with serial sampling, three baselines will be derived for all predose, mean morning, and mean 24-hour values where a change from baseline calculation is necessary, unless otherwise specified. Baseline pre-dose will be defined as the average of the 0600 and 0800 timepoint values at the baseline visit. Baseline mean morning will be defined as the average of the 0600, 0800, +3 hours post-dose, and +6 hours post-dose timepoint values at the baseline visit. Baseline mean 24-hour will be defined as the average of all timepoints at the baseline visit.

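### The double-blind C-SSRS shift table compares a baseline of a few weeks with a maximum over about 28 weeks and leaves out the past-6-month screening score, so recurring ideation can be displayed as new

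*SAP*

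**What the plan says.** SAP 11.6 plans a 6 x 6 table of ideation scores (0 to 5) by treatment group, "with the rows representing the baseline score and the columns representing the maximum score recorded across all postbaseline assessments", with unscheduled visits included. The section does not say what the baseline score is. That comes from SAP 6.3.1, where "the assessments collected on Day 1 prior to the first dose of study drug in the DB period will serve as the baseline value". The C-SSRS is not among the endpoints with their own baseline (SAP 6.3.3 to 6.3.5), and SAP 11.6 itself labels Day 1 as the baseline assessment in its list of summaries. A screening value can enter only as a fallback: "If a Day 1 baseline value is not available, then the last measurement collected prior to study drug will serve as baseline".

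Protocol Table 7, footnote s, fixes the form by visit: "Baseline/Screening version used at screening, and Since Last Visit version at subsequent visits". Protocol 9.8.2.1 confirms it for Day 1: "C-SSRS (Since Last Visit version; only for subjects ≥6 years". The Day 1 form therefore looks back to the screening administration and no further. Protocol 9.8.1.1 gives that interval: "Subjects will undergo screening for up to 4 weeks (Week -4 to Day -1) to determine eligibility", and "The screening period can be extended by up to 4 weeks after discussion with and approval of the Medical Monitor".

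The longer history is collected. SAP 11.6 lists a separate summary, "Screening/past 6 months (suicidal ideation items); past 1 year (suicidal behavior items) assessment", but does not carry that score into the shift rows. Exclusion 15 (Protocol 8.2) removes children with type 4 or 5 ideation in the 6 months before screening or with any lifetime suicidal behavior. Types 1 to 3 are not excluded.

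**The concern.** The row and the column of one table describe periods of very different length. Take a child with type 2 ideation three months before screening, none between screening and Day 1, and type 2 again at Week 16. The planned table counts that child as a 0-to-2 shift, although the database holds a score showing that the ideation is not new. The past-6-month summary does not repair this, because it gives group counts that cannot be matched to shift cells.

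At stake is how a descriptive safety display is read, in a programme that monitors suicidality closely. Protocol 5.2 reports C-SSRS ideation by arm from the depression study, and SAP 7.4.1 lists depression and anxiety among the conditions of interest, so some earlier low-grade ideation is foreseeable. A 0-to-positive cell will naturally be read as ideation that began on study drug.

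**Working it through.** The plan gives no rate, sample size or power for this table, so there is no figure to reproduce. The windows come from the documents. The event rates below are assumptions for illustration only.

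**Windows, double-blind period**
- Row: 4 weeks, or 8 with extended screening (Protocol 9.8.1.1).
- Column: 28 weeks (C-SSRS at Weeks 4, 16 and 28 in Protocol Table 7, plus unscheduled visits).
- Ratio: 28/4 = 7, or 28/8 = 3.5.
- Row with the past-6-month score added: about 26 + 4 = 30 weeks, against 28.

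**Check 1: the same constant risk in every child, no drug effect.** Let p be the chance of ideation per 4 weeks, q = 1 - p, and n the row window in 4-week units. Then P(0 to positive) = q^n x (1 - q^7) and P(positive to 0) = (1 - q^n) x q^7. For example, p = 0.01 and n = 1 give 0.99 x (1 - 0.99^7) = 0.99 x 0.0679 = 0.0673.

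| p | n (row window) | 0 to positive | positive to 0 | ratio |
|---|---|---|---|---|
| 0.01 | 1 (4 weeks) | 6.7% | 0.9% | 7.2 |
| 0.01 | 2 (8 weeks) | 6.7% | 1.9% | 3.6 |
| 0.01 | 7.5 (30 weeks) | 6.3% | 6.8% | 0.93 |
| 0.02 | 1 (4 weeks) | 12.9% | 1.7% | 7.4 |
| 0.02 | 2 (8 weeks) | 12.7% | 3.4% | 3.7 |
| 0.02 | 7.5 (30 weeks) | 11.3% | 12.2% | 0.93 |

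The longer row window lowers 0-to-positive shifts only from 6.7% to 6.3%, or from 12.9% to 11.3%. The ratio falls mainly because positive-to-0 shifts rise. If risk does not vary between children, past ideation says nothing about later ideation.

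**Check 2: a recurrent subgroup (one assumed mixture).** 10% of children have p = 0.15 per 4 weeks and 90% have p = 0.002.
- Day 1 row: 0.10 x 0.85 x (1 - 0.85^7) + 0.90 x 0.998 x (1 - 0.998^7) = 0.0578 + 0.0125 = 7.0%.
- Row with the past-6-month score: 0.10 x 0.85^7.5 x (1 - 0.85^7) + 0.90 x 0.998^7.5 x (1 - 0.998^7) = 0.0201 + 0.0123 = 3.2%.
- Relative fall: (7.0 - 3.2)/7.0 = 54%.

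**Check 3: one child with recurrent ideation.** Episodes occur at constant rate r per week, with no drug effect. P(0 to positive) = exp(-r x row weeks) x (1 - exp(-28r)). With a mean gap of 3 months (13 weeks), the Day 1 row gives exp(-4/13) x (1 - exp(-28/13)) = 0.735 x 0.884 = 0.65, and the 30-week row gives exp(-30/13) x 0.884 = 0.09.

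| Mean gap | Day 1 row, 4-week screening | Day 1 row, 8-week screening | Worse of past 6 months and Day 1 (4-week screening) |
|---|---|---|---|
| 1 month | 0.40 | 0.16 | 0.001 |
| 3 months | 0.65 | 0.48 | 0.09 |
| 6 months | 0.57 | 0.49 | 0.21 |
| 12 months | 0.39 | 0.36 | 0.23 |

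**Open-label period.** SAP 11 uses period-specific baselines, so the row is the Week 28 score, looking back to Week 16 (about 12 weeks), against 24 weeks to Week 52. In the Check 1 model, with 3 units before and 6 after, the ratio is about 2.0 to 2.1.

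**The case against.** The strongest reply is that little depends on this table. SAP 11 makes all safety analyses descriptive, with no hypothesis tests. The safety endpoint in SAP 4.6 is any positive postbaseline response, not a shift. SAP 11.6 also tabulates lifetime, past-6-month, Day 1 and postbaseline responses, and never calls a shift cell new. Clinically significant ideation is recorded as an adverse event (Protocol 11.1), and the TEAE definition in SAP 11.2 separates new events from worsening ones. For safety monitoring, a Day 1 baseline errs toward showing a change. A longer baseline would display a recurrence on drug as no change. Most of this stands. It argues for keeping the planned table, but not against adding one that uses the history already collected.

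A reader might also infer more than the documents support:

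- **That the randomised comparison is biased.** Both arms have the same windows, so by design it is not.
- **That a 7:1 excess of worsening measures falsely new ideation.** It holds for 4-week screening and is about 3.6:1 at 8 weeks. Check 1 shows that it can occur when almost no pre-existing ideation is shown as new.
- **That serious ideation is mislabelled.** In an eligible child, a postbaseline type 4 or 5 is a real rise over the past 6 months. The problem concerns types 1 to 3.
- **That the open-label baseline should become the maximum of all scores before the first crinecerfont dose.** That would look back about 30 weeks in the crinecerfont/crinecerfont group but about 30 + 28 = 58 weeks in the placebo/crinecerfont group. With n = 58/4 = 14.5 and 6 units after, the Check 1 model gives 0.38 to 0.40 worsening per improvement in former-placebo children, a false excess of improvement of about 2.5:1. That is larger than the artefact it would replace, and it differs between the groups.

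**Conclusion.** The mismatch is real and follows from the text: a row of at most 4 weeks (8 if extended), a column of about 28 weeks, and a past-6-month score that is collected but not used in the row unless the Day 1 fallback brings in screening. The double-blind table can therefore overstate new type 1 to 3 ideation within each arm.

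The documents do not fix the size. It runs from negligible (0.4 to 1.6 percentage points in Check 1) to roughly half of the apparent new cases in the single mixture of Check 2, whose inputs are assumed. Any count should use only children aged 6 or over, since younger children are not rated. The full planned arm of 54 is too large a denominator.

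This is an inexpensive improvement to a safety display. It does not affect any efficacy conclusion or the between-arm safety comparison.

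**What to change.** In SAP 11.6:

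- State that the planned double-blind shift table uses the Day 1 score, and give its look-back.
- Add a second double-blind shift table, shown beside it, whose row is the maximum of the screening past-6-month ideation score and the Day 1 score. Describe ideation as new only relative to that row.
- Keep the Week 28 baseline for the open-label table, with a footnote that it looks back about 12 weeks against about 24 weeks of follow-up.

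The cost is a few sentences, one extra table and its programming, with no new data. In the added table a recurrence at the same level appears as no change, which is why the Day 1 table should stay.
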